4.2. Determination of Sample Size

The primary purpose of this Phase 2 study is to assess the safety of ALPN-101 in subjects with moderate to severe SLE. As such, the anticipated sample size of 130 subjects randomized 1:1 to receive ALPN-101 or placebo was not derived to support formal hypothesis testing of efficacy endpoints.

Table 1 provides the estimated power to detect a range of potential differences in proportions. For these calculations, a sample size of 65 subjects per treatment group, a two-sided chi-square test statistic and a significance level (alpha) of 0.05 were used. Placebo response rates of 40% for SRI-4 and 20% for BICLA and effect sizes ranging from 15% to 35% were assumed.

No adjustments for multiplicity are planned for this early phase study.

SRI-4			BICLA		
Response Rate		Estimated	Response Rate		Estimated
Placebo	ALPN-101	Power*	Placebo	ALPN-101	Power*
40%	55%	40%	20%	35%	48%
40%	60%	63%	20%	40%	71%
40%	65%	82%	20%	45%	87%
40%	70%	94%	20%	50%	96%
40%	75%	99%	20%	55%	99%

Table 1: Estimated Power Based on N=65 Subjects per Treatment

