4. STUDY DESIGN

4.1. General Description

This is a Phase 2, multicenter, multinational, randomized, double-blind, placebo-controlled, parallel-group study to evaluate the safety, tolerability, efficacy, immunogenicity, PK at LPN-101 compared to placebo in adult subjects with chronic, moderate to severe active SLE. At least 130 subjects will be randomized in a 1:1 ratio to receive a weight-based dose of 3 mg/kg ALPN-101 administered by intravenous infusion via an infusion pump or matching placebo every other week (Q2W) for a total of 12 doses. An overview of the study design is provided in Appendix 15.1.

Randomization will be stratified based by SLE treatment at baseline and geographic region (Appendix 15.5). Subjects will be followed for 4 weeks after the End of Treatment (EOT) visit, 6 weeks after the last dose of study drug. Assessments of adverse events (AEs) and disease activity, and collection of blood and urine for safety laboratory values, biomarkers of disease activity, PK, ADA, and will be performed throughout the study. The Schedule of Assessments is provided in Appendix 15.2.

Each subject will participate for up to 34 weeks, including:

- Screening Period: Up to 42 days prior to first dose date. All subjects must complete all screening assessments and make them available to the team for verification of disease activity. Subjects who appear to meet eligibility criteria must undergo central review and verification of SLE disease activity prior to randomization.
- Treatment Period: Up to 24 weeks from first dose date. Subjects will receive 12 doses of study treatments Q2W. Safety, biologic activity, PK, ADA, will be conducted according to the Schedule of Assessments (Appendix 15.2).
- Follow-up Period: 4 weeks after EOT.

Dense PK will be collected in subjects who agree to participate. Additional PK samples will be collected from these subjects 4 hours following administration of the first dose of study drug, and on days 1, 3 and 7 following the first study drug administration.

Medications that are used for treatment of SLE at baseline should be maintained at stable doses through the Day 169 assessments, except for incidences of toxicity or for a protocol-defined short-term increase (burst and taper) of corticosteroid dose in response to increased disease activity or reduction in corticosteroids (taper) to reduce toxicity in the context of improvement in disease activity.

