Subjects who prematurely discontinue treatment with study drug should have all procedures outlined in the EOT visit and an unscheduled ECG performed as soon as possible, and not later than the next scheduled visit. To minimize missing data for efficacy and safety assessments, subjects who prematurely discontinue treatment, and who do not withdraw from the study, should otherwise continue their regular study visit schedule without receiving study drug. In subjects who are unable to continue their regularly scheduled visits, a follow-up phone call should occur approximately 8 weeks (corresponding to 5X half-life) after the last dose of study drug to determine the status of any ongoing AEs/ SAEs or the occurrence of any new AEs/SAEs.

Subjects who withdraw from the study prematurely (i.e., prior to Day 197), the End of Study (EOS) evaluations should be completed, if possible, preferably within 2 weeks of study drug discontinuation. In addition, a follow-up phone call should occur approximately 8 weeks (corresponding to 5x half-life) after the last dose of study drug to determine the status of any ongoing AEs/SAEs or the occurrence of any new AEs/SAEs.

It should be noted that while N=130 subjects were expected to be randomized in this study, enrollment was stopped at N=76 subjects.

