5. ANALYSIS POPULATIONS AND SUBGROUPS

5.1. Analysis Populations

The following analysis populations will be used for the analysis of study data.

- All Randomized Population: The randomized population will include all subjects who are assigned to study treatment, regardless of whether study treatment is received. The randomized population will be analyzed according to the treatment group into which they were randomized, regardless of the actual treatment received.
- Modified Intent-to-Treat Population: The modified intent-to-treat (mITT) population includes all randomized subjects who received any amount of study drug and completed at least one post-baseline disease assessment. mITT subjects will be analyzed according to the treatment group into which they were randomized, regardless of the actual treatment received. Unless otherwise specified, this population will be used for the analysis of efficacy endpoints.
- **Safety Population:** The safety population includes all subjects who received any amount of study drug. The safety population will be analyzed by treatment actually received. Unless otherwise is specified, this population will be used for the analysis of safety endpoints.
- **Pharmacokinetics Population:** The PK population includes all subjects who received at least one dose of ALPN-101 and have at least one post-dose PK concentration reported. Unless otherwise is specified, this population will be used for the analysis of PK endpoints.
- Anti-Drug Antibodies Population: The ADA population includes all subjects who received at least one dose of study drug and have at least one post-baseline ADA value.

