7.4. Analysis of Efficacy Endpoints

7.4.1. General Considerations

Unless otherwise stated, all efficacy analyses will be conducted on the mITT population according to the randomized treatment. For efficacy endpoints, point estimates of treatment differences and 95% confidence intervals (CI) will be provided. Two-sided p-values will also be provided for efficacy endpoints, as applicable. Where possible, study outcomes will be presented graphically also. Due to small sample sizes of subjects randomized to the Asia geographic region, this region will be pooled with the Eastern Europe region in the statistical analysis models.

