7.5. Analysis of Primary Efficacy Endpoints

7.5.1. Main Analysis

Response rates for subjects in the ALPN-101 group and in the placebo group will be calculated and the corresponding 95% CI will be reported for each treatment group. These response endpoints will be analyzed through Day 169 for subjects who complete treatment and through

the last assessment recorded ≤28 days after treatment discontinuation date for subjects who discontinue treatment early.

For the main analyses of SRI-4 response rate and BICLA response rate, non-responder imputation will be used for IE and missing data as described in Section 7.4.2.

Response rates will be compared using Cochran-Mantel-Haenszel (CMH) test statistic stratified by the factors used at randomization. Estimated treatment effect will be reported as the difference between the response rate in the ALPN-101 treatment group and the response rate in the placebo group. Corresponding 95% CI for the difference in proportions and the two-sided p-value for the difference will be reported.

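### SAP 4.2 gives efficacy power only for 65 per arm, although SAP 4.1 records that enrolment stopped at 76; at an assumed 38 per arm the 82% and 87% become about 59% and 65%

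*SAP*

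**What the plan says.** SAP 4.1 opens with the design size in the future tense: "At least 130 subjects will be randomized in a 1:1 ratio". The same section ends by noting that "while N=130 subjects were expected to be randomized in this study, enrollment was stopped at N=76 subjects".

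SAP 4.2 follows directly. It calls 130 the anticipated size, says that this number "was not derived to support formal hypothesis testing of efficacy endpoints", and presents Table 1 for "a sample size of 65 subjects per treatment group, a two-sided chi-square test statistic" at alpha 0.05. With placebo rates of 40% (SRI-4) and 20% (BICLA), Table 1 gives 82% and 87% power for a 25-point difference. Protocol 10.2 carries the same two percentages for 65 per arm. Neither document gives power, a detectable difference or an expected precision for 76 subjects.

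The SAP names SRI-4 and BICLA response at Day 169 as its primary efficacy endpoints (SAP 3.1.1). SAP 7.5.1 fixes the test: "Response rates will be compared using Cochran-Mantel-Haenszel (CMH) test statistic stratified by the factors used at randomization". It also fixes the reporting: "Corresponding 95% CI for the difference in proportions and the two-sided p-value for the difference will be reported".

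One analysis section already reflects the subjects actually randomized. SAP 7.4.1 states: "Due to small sample sizes of subjects randomized to the Asia geographic region, this region will be pooled with the Eastern Europe region".

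**The concern.** The SAP was edited after enrolment stopped, but the opening size sentence of 4.1 and the power figures of 4.2 were left at the planned size. A reader who turns to 4.2 to see what the two Day 169 comparisons can detect finds 82% and 87% for a 25-point benefit, and nothing else.

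The risk lies in interpretation. If a non-significant SRI-4 or BICLA result is read against Table 1, it looks like fair evidence against a 25-point effect. At the attained size it is much weaker evidence, because a real effect of that size would be missed far more often than Table 1 implies.

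**Working it through.** **Inputs**
- From SAP 4.2: two-sided chi-square test, alpha 0.05, SRI-4 40% vs 65%, BICLA 20% vs 45%, n = 65 per arm.
- From SAP 4.1: 76 randomized.
- Assumption: an even 38/38 split under 1:1 allocation. The actual split is not given.

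**Formula.** Pooled-variance normal approximation without continuity correction, with d = p₂ − p₁ and p̄ the mean of the two rates:

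power = Φ{ [d − 1.96·√(2p̄(1−p̄)/n)] / √([p₁(1−p₁)+p₂(1−p₂)]/n) }

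**Step 1: reproduce Table 1 at n = 65**
- SRI-4: p̄ = 0.525. (0.25 − 1.96·√(0.49875/65)) / √(0.4675/65) = (0.25 − 0.1717)/0.0848 = 0.923, so power is 82.2%.
- BICLA: p̄ = 0.325. (0.25 − 1.96·√(0.43875/65)) / √(0.4075/65) = (0.25 − 0.1610)/0.0792 = 1.124, so power is 86.9%.

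Both match the stated 82% and 87%. All ten Table 1 entries reproduce to the rounded percent, so this is the table's own convention.

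**Step 2: the same formula at n = 38**
- SRI-4: (0.25 − 1.96·√(0.49875/38)) / √(0.4675/38) = (0.25 − 0.2245)/0.1109 = 0.230, so power is 59.1%.
- BICLA: (0.25 − 1.96·√(0.43875/38)) / √(0.4075/38) = (0.25 − 0.2106)/0.1036 = 0.380, so power is 64.8%.

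Table 1 recomputed at 38 per arm:

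| Difference (points) | 15 | 20 | 25 | 30 | 35 |
|---|---|---|---|---|---|
| SRI-4, 65 per arm (SAP) | 40% | 63% | 82% | 94% | 99% |
| SRI-4, 38 per arm | 26% | 41% | 59% | 76% | 89% |
| BICLA, 65 per arm (SAP) | 48% | 71% | 87% | 96% | 99% |
| BICLA, 38 per arm | 31% | 48% | 65% | 79% | 90% |

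**Step 3: detectable difference and precision.** The detectable difference solves the formula for 80% power. The half-width is the Wald value at the 25-point effect, 1.96·√([p₁(1−p₁)+p₂(1−p₂)]/n); for SRI-4 at 38 per arm, 1.96 × 0.1109 = 0.217.

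| Per arm | Detectable, SRI-4 / BICLA (points) | Half-width, SRI-4 / BICLA (points) |
|---|---|---|
| 65 | 24.3 / 22.6 | 16.6 / 15.5 |
| 38 | 31.4 / 30.2 | 21.7 / 20.3 |
| 34 | 33.1 / 32.1 | 23.0 / 21.5 |

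**Step 4: sensitivity (25-point difference)**
- Uneven split: power stays at 58.5–59.1% (SRI-4) and 63.7–65.0% (BICLA) for splits of 76 from 34/42 to 42/34.
- Exact enumeration of the uncorrected chi-square test at 38 per arm: 59.8% and 65.9%. With a continuity correction it would be lower, 49.7% and 55.0%, but that convention does not reproduce Table 1.
- The planned test is a stratified CMH, not the unstratified chi-square of Table 1. Simulation at N = 76 with four assumed strata (therapy by pooled region) gives 60–61% and 65–67%. With six unpooled strata it gives about 59–60% and 65%.
- Analysis population: mITT takes "all randomized subjects who received any amount of study drug and completed at least one post-baseline disease assessment", so it may be smaller than 76. Its size is not given. At an assumed 34 per arm, power is 54% and 60%.

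**Illustration.** With 15/38 placebo responders (39.5%) and 20/38 active (52.6%), the difference is 13.2 points, the Wald 95% interval runs from −9.1 to 35.4, and p = 0.25. That result is not significant, yet it is compatible with the full 25-point effect.

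**The case against.** The strongest reply is that nothing is concealed and nothing in the analysis is affected. SAP 4.1 discloses the stop, so nobody reading the whole section could believe that 130 were enrolled. Section 4.2 already calls 130 anticipated, Table 1 is titled with its n of 65, and its figures are right for that n. A sample size section records the planning rationale, which early closure does not make false. Safety is the primary objective and is described without formal inference. No success or futility threshold on SRI-4 or BICLA is stated. The pooling of Asia had to be written down because it changes the models; power rows change no model. Once results exist, the observed confidence intervals will show the precision directly.

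Most of this stands, and it limits the point to reporting. It does not remove it. Disclosing the stop does not tell the reader what 76 subjects can detect, and the only figures on that question describe a trial of a different size. Table 1's title helps, but the reader must still notice that 65 per arm was not attained and redo the calculation. The added figures would not be observed power: they use the SAP's own assumed rates and effects with the attained n, and no outcome data. It is also fair to say that the split, the strata and the mITT size are all assumed. The sensitivity results show that split and stratification hardly matter, and that a smaller mITT population only lowers power further.

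**Conclusion.** The concern holds. The size sentence in SAP 4.1 and the power figures in SAP 4.2 describe a trial that was not delivered, and the SAP gives nothing in their place. At an assumed 38 per arm, with Table 1's rates and method, a true 25-point benefit would be missed about 41% of the time for SRI-4 (100 − 59.1) and 35% for BICLA (100 − 64.8). Table 1 implies about 18% and 13%.

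The consequence is confined to interpreting the two efficacy comparisons. No estimate, test, population or decision rule is wrong because of it, and the primary safety objective is untouched. It should be corrected, but it does not threaten the trial's conduct.

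**What to change.** - **SAP 4.1:** replace the future-tense statement of at least 130 with the planned size of 130 and the attained size of 76.
- **SAP 4.2:** mark Table 1 as the planned, not attained, size. The word planned in the title and a short sentence suffice.
- **SAP 4.2:** add, for the attained size, the power at each Table 1 difference, the difference detectable with 80% power (about 31 points for SRI-4 and 30 for BICLA), and the expected 95% confidence interval half-width at 25 points (about ±22 and ±20).
- **SAP 4.2:** state that these figures assume 38 per arm, that they use the unstratified chi-square as an approximation to the planned CMH test, and that the mITT population may be smaller.

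The cost is a few sentences and table rows. No patients, data or unblinding are needed, because the total of 76 and the 1:1 ratio are enough. The one drawback for the sponsor is that the stated figures become less favourable.

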4.3. Methods of Assigning Subjects to Treatment

A centralized interactive web-based response system will be used to randomly assign subjects to receive either ALPN-101 or placebo in a 1:1 ratio. Randomization will be stratified by geographic region and by use of concomitant oral immunosuppressive therapy at enrollment. Levels of each stratification factor, which result in 6 unique strata, are defined as follows:

- 1. Background immunosuppressive therapy use:
 - Present: Concomitant use of at least one of the permitted immunosuppressants (e.g., methotrexate, leflunomide, azathioprine, 6-mercaptopurine, mycophenolate mofetil, mycophenolic acid) and/or corticosteroids at doses >5 mg prednisone or equivalent daily with or without hydroxychloroquine/hydroxychloroquine-like drugs;

^{*}Assuming a 2-sided significance level of 0.05 using SAS version 9.4

• Absent: No use of permitted immunosuppressants and/or corticosteroids at doses >5 mg prednisone or equivalent daily, with or without use of lower doses of corticosteroids and/or hydroxychloroquine/hydroxychloroquine-like drugs.

2. Geographic region:

- Region 1: North America or Western Europe
- Region 2: Eastern Europe
- Region 3: Asia

Subjects, investigators, site staff, and individuals with direct contact with site staff (e.g., clinical research associates, project management, medical monitors, and data management) will remain blinded to treatment assignment until after final database lock. Select study team members may be unblinded to treatment assignment. A list of all individuals unblinded to treatment assignment prior to final database lock will be maintained.

5. ANALYSIS POPULATIONS AND SUBGROUPS

5.1. Analysis Populations

The following analysis populations will be used for the analysis of study data.

- All Randomized Population: The randomized population will include all subjects who are assigned to study treatment, regardless of whether study treatment is received. The randomized population will be analyzed according to the treatment group into which they were randomized, regardless of the actual treatment received.
- Modified Intent-to-Treat Population: The modified intent-to-treat (mITT) population includes all randomized subjects who received any amount of study drug and completed at least one post-baseline disease assessment. mITT subjects will be analyzed according to the treatment group into which they were randomized, regardless of the actual treatment received. Unless otherwise specified, this population will be used for the analysis of efficacy endpoints.
- **Safety Population:** The safety population includes all subjects who received any amount of study drug. The safety population will be analyzed by treatment actually received. Unless otherwise is specified, this population will be used for the analysis of safety endpoints.
- **Pharmacokinetics Population:** The PK population includes all subjects who received at least one dose of ALPN-101 and have at least one post-dose PK concentration reported. Unless otherwise is specified, this population will be used for the analysis of PK endpoints.
- Anti-Drug Antibodies Population: The ADA population includes all subjects who received at least one dose of study drug and have at least one post-baseline ADA value.

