10.4. Analysis Populations

- Modified Intent-To-Treat (mITT) Population: all randomized subjects who received any amount of study drug and completed at least one post-baseline disease assessment. mITT subjects will be analyzed according to the treatment arm into which they were randomized regardless of the actual treatment received. The mITT is the analysis population for the primary efficacy analysis.
- **Safety Population:** all randomized subjects, classified according to the actual treatment received, who received any amount of study drug and have at least one post-baseline safety evaluation. This is the primary analysis population for the safety analysis.
- PK Population: all subjects who received ≥ 1 dose of ALPN-101 and have ≥ 1 post-dose PK concentration reported.

Other analysis populations may be defined in the SAP.

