7.4.2. Handling of Missing Data and Intercurrent Events (IE)

Intercurrent events in this study include the following:

- IE1: Premature discontinuation of study treatment
- IE2: Restricted/rescue medication use (criteria for restricted/rescue medication use is provided in Section 6.21)

The strategies to be used in the handling of intercurrent events and missing data for efficacy endpoints, when applicable, are provided below:

- Binary endpoints (primary and secondary efficacy endpoints):
 - IE1 and IE2: subject is considered a non-responder (composite strategy)
 - Missing data for Day 169: subject is considered a non-responder
- Continuous endpoints measured through time (SLEDAI-2K total score):
 - IE1 and IE2: data after IE1 and IE2 occurs will not be included in the analysis (hypothetical strategy)
 - Missing data caused by applying the intercurrent event handling described above and other missing data will be handled by the mixed effects models for repeated measures (MMRM) analysis
- Other efficacy endpoints:
 - Treatment policy strategy will be applied and all observed data during the treatment period will be used regardless of IE1 or IE2
 - Missing data for Day 169 for binary endpoints: subject is considered a non-responder for applicable endpoints

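### For the binary endpoints scored by non-responder imputation, the mITT condition drops dosed subjects whom the SAP's own missing-data rule would count as non-responders

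*SAP*

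**What the plan says.** SAP 5.1 defines the mITT population as "all randomized subjects who received any amount of study drug and completed at least one post-baseline disease assessment". The part at issue is the last condition, that the subject "completed at least one post-baseline disease assessment". Protocol 10.4 sets the same condition and adds: "The mITT is the analysis population for the primary efficacy analysis". SAP 7.4.1 states that, unless otherwise specified, "all efficacy analyses will be conducted on the mITT population according to the randomized treatment".

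For the binary primary and secondary endpoints, SAP 7.4.2 gives two rules that both lead to failure. The first intercurrent event is "IE1: Premature discontinuation of study treatment", and a subject who has it is a non-responder under a composite strategy. Absent data are covered separately: "Missing data for Day 169: subject is considered a non-responder". SAP 7.5.1 carries this into the main analyses of SRI-4 and BICLA, where "non-responder imputation will be used for IE and missing data as described in Section 7.4.2". SAP Table 2 repeats the handling for SRI-4, BICLA, LLDAS and the CLASI 50% endpoint. It describes the estimand population simply as patients with moderate to severe disease.

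SAP 5.1 also defines an All Randomized and a Safety population. The available text assigns no efficacy analysis to either.

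**The concern.** A requirement for post-baseline data makes sense when an analysis needs an observed value. Non-responder imputation does not: every dosed subject has an outcome whether or not anyone assessed them. The mITT condition therefore takes out only subjects whose imputed result is already fixed as failure, and it selects them on something that happens after randomisation.

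At stake are the response rates, the difference in proportions, its confidence interval and the p-value that SAP 7.5.1 commits to report. Each exclusion raises the response rate of the arm it comes from. With enrolment stopped at 76 (SAP 4.1), a few subjects can shift the estimate visibly. The CLASI 50% endpoint is restricted to baseline activity scores of 8 or more, so each subject weighs more there.

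**Working it through.** **1. The rules side by side.** Take a subject who is dosed and has no disease assessment afterwards.

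- SAP 7.4.2: no Day 169 result, so non-responder. If treatment also stopped early, non-responder on that ground too.
- SAP 5.1: no post-baseline assessment, so not in mITT.
- SAP 7.4.1: efficacy is analysed on mITT, so the subject counts in neither numerator nor denominator.

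**2. Who can be affected.** The first scheduled post-baseline assessment is SLEDAI-2K and PhGA at Day 15 (Protocol 6.4.1); BILAG follows at Day 29 (Protocol 6.4.2). To be excluded, a dosed subject must miss Day 15 and everything later, and must also complete no End of Treatment, End of Study or unscheduled disease assessment. The SAP does not define the term disease assessment. If it were read as BILAG only, losses between Day 15 and Day 29 could be added.

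**3. The plan's own figures.** SAP Table 1 gives 82% power for 40% versus 65% and 87% for 20% versus 45%, with 65 per arm. Using the two-sided chi-square approximation with p̄ the mean rate,

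z = [Δ − 1.96·√(2p̄(1−p̄)/n)] / √([p₁(1−p₁)+p₀(1−p₀)]/n)

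- SRI-4: (0.25 − 1.96×0.0876)/0.0848 = 0.92, power 82.2%.
- BICLA: (0.25 − 1.96×0.0822)/0.0792 = 1.12, power 86.9%.

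Both reproduce. They do not depend on the mITT condition; they serve only to anchor the rates below.

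**4. Illustration of size.** Inputs from the SAP: 76 randomised (4.1), and Table 1 rates of 65% versus 40% for SRI-4 and 45% versus 20% for BICLA. Assumptions not in the documents: an even split with everyone dosed (76/2 = 38 per arm), and 0 to 3 exclusions per arm. The nearest whole responder counts are 25 and 15 for SRI-4 (0.65×38 = 24.7; 0.40×38 = 15.2), and 17 and 8 for BICLA (0.45×38 = 17.1; 0.20×38 = 7.6).

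Excluding k non-responders changes an arm's rate from x/n to x/(n−k). With k = 3, the denominator falls from 38 to 35.

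| Excluded (ALPN-101, placebo) | SRI-4 rates | SRI-4 difference | BICLA rates | BICLA difference |
|---|---|---|---|---|
| 0, 0 (all treated) | 65.8% vs 39.5% | 26.3 | 44.7% vs 21.1% | 23.7 |
| 3, 0 | 71.4% vs 39.5% | 32.0 | 48.6% vs 21.1% | 27.5 |
| 0, 3 | 65.8% vs 42.9% | 22.9 | 44.7% vs 22.9% | 21.9 |
| 3, 3 | 71.4% vs 42.9% | 28.6 | 48.6% vs 22.9% | 25.7 |

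Differences are in percentage points, computed before rounding. For SRI-4, the unadjusted chi-square p-values down the four rows are 0.022, 0.006, 0.049 and 0.016. The planned test is a stratified CMH, so these only indicate scale.

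With no true difference (15 of 38 in each arm), dropping three ALPN-101 subjects gives 15/35 − 15/38 = 42.9% − 39.5% = 3.4 points from the denominator alone.

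**The case against.** The strongest reply is that the exclusion will rarely bite. Stopping study drug does not remove anyone from mITT. Protocol 4.3.2 and 6.6.1 ask early stoppers for the full End of Treatment procedures soon after stopping and then for the regular visits. Those procedures include BILAG, SLEDAI-2K 30, PhGA and CLASI (Protocol 6.4.12). Subjects who withdraw consent are asked for End of Study evaluations where possible. A reader might infer that someone who stops after an early infusion reaction disappears from the analysis. The documents point the other way: that subject would usually be assessed, enter mITT and count as a non-responder. This stands, and it confines the point to a narrow group.

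Second, a single mITT set serves every efficacy endpoint, and MMRM and the BILAG flare rate cannot use a subject with no follow-up data. That is a reason for the condition on those endpoints. It does not carry over to endpoints where the outcome is imputed by rule.

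Third, SAP 7.1 already reports the number treated and the number in each population by arm, so any gap will be visible. That helps the reader but leaves the planned estimate, interval and p-value on the reduced denominator. The SAP contents also list a section on robustness of the imputation method (7.5.2.1), whose text is not in the public copy. A sensitivity analysis there cannot be ruled out, but it would not alter the main denominator.

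Finally, safety is the primary objective, and the sample size was not derived for formal efficacy testing (SAP 4.2). That limits the weight of the point without removing it.

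**Conclusion.** The point holds for SRI-4, BICLA, LLDAS and the CLASI 50% endpoint. The mITT condition removes dosed subjects whom SAP 7.4.2 would score as failures, so the denominator rests on a post-randomisation event. It does not apply to the SLEDAI-2K MMRM or the treatment-policy endpoints.

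The size is uncertain and probably small. Under the stated assumptions, up to three exclusions in a single arm shift the difference by −3.4 to +5.6 points for SRI-4 and by −1.8 to +3.8 points for BICLA. Three exclusions would mean 3/38 = 7.9% of an arm dosed and never assessed again. With no exclusions there is no effect.

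Two stronger readings are not supported. One is that the rule favours ALPN-101: the direction depends on which arm loses subjects, and the documents give no counts. The other is that the analysis set contradicts the estimand: Table 2 names a target population, which is a different thing from an analysis set, and protocol and SAP agree on mITT. The conflict is with the missing-data rule.

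**What to change.** In SAP 5.1 and 7.4.1, specify that the binary endpoints under non-responder imputation are analysed on all randomised subjects who received any study drug, by randomised arm, with missing outcomes counted as non-response. For the CLASI 50% endpoint, apply this within the subgroup with baseline activity score of 8 or more. The Safety population cannot simply be reused, because it is analysed by treatment received. Keep mITT as written for the MMRM and treatment-policy endpoints, and as a sensitivity set for the binary ones.

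The cost is a short SAP edit and an entry in SAP Section 8, since Protocol 10.4 names mITT for the primary efficacy analysis. Protocol 10.1 gives the SAP precedence, and no new data are needed. Response rates may come out slightly less favourable, and binary and continuous endpoints may have slightly different denominators, which a table footnote can explain.
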